9.1.2 Visit 2, Baseline (Day 0)

Subjects will return for Visit 2 up to 28 days after Visit 1. The interval may be extended, if necessary and after discussion with the Axsome Medical Monitor, to accommodate medication washout or repeat screening procedures. The following procedures will be performed at Baseline (Day 0):

- Review and confirm inclusion/exclusion criteria.
- Record vital signs, including: Blood pressure, pulse, respiratory rate, and oral temperature after subject has been seated for 5 minutes.
- Review and record AEs since last visit.
- Review and record any current concomitant medication use (including OTC, vitamins, and supplements).
- Collect urine sample for on-site drug screening and urine pregnancy test (if female).
- •
- Administer evaluations:
 - MADRS (≥ 25 inclusive)
 - \circ CGI-S (\geq 4 inclusive)
 - o QIDS-SR-16
 - C-SSRS (since last visit)
- Randomize subject once it is determined that subject satisfies all of the inclusion and exclusion criteria (on the basis of the screening and baseline assessments described above). Eligible subjects will be randomized sequentially and assigned the corresponding kit number.
- Dispense 1 study drug bottle from the subject assigned kit.
- Instruct subject to begin to dose 1 tablet the following morning for the next three days, on an empty stomach (at least 2 hours pre- or 2 hours post-prandial), orally with water.
- Schedule Visit 3 telephone call for Day 3.
- •

9.1.3 Visit 3 (Day 3)

The following procedures will be performed via telephone at Visit 3 (Day 3):

- Review and record AEs since last visit.
- Review and record any current concomitant medication use (including OTC, vitamins, and supplements).
- Review study drug compliance and confirm QD dosing for 3 days.
- Instruct subject to begin BID dosing on Day 4 (the day after the call or the day of if calling on Day 4). Confirm doses will be taken at least 8 hours apart, orally on an empty stomach (at least 2 hours pre- or 2 hours post-prandial) with water.

•

9.1.4 Visit 4, 5, 6, and 7 (Days 7, 14, 21, and 28)

The following procedures will be performed at Visits 4 – 7 (Days 7, 14, 21, and 28):

- Record vital signs, including: Blood pressure, pulse, respiratory rate, and oral temperature after subject has been seated for 5 minutes.
- Review and record AEs since last visit.
- Review and record any current concomitant medication use (including OTC, vitamins, and supplements).
- •
- Collect all unused study drug dispensed at previous visit.
- Assess study drug compliance via drug accountability. Noncompliant subjects may be discontinued.
- Dispense and/or redispense study drug bottle(s) to subject from the previously assigned kit.

•

- Administer evaluations:
 - o MADRS
 - QIDS-SR-16
 - o CGI-S
 - o CGI-I
 - C-SSRS (since last visit)
- Remind subject to continue dosing BID at least 8 hours apart, orally on an empty stomach (at least 2 hours pre- or 2 hours post-prandial) with water.

9.1.5 Visit 8 (Day 42) / Early Termination

The following procedures will be performed at Visit 8 (Days 42) or the Early Termination Visit:

- Record vital signs, including: Blood pressure, pulse, respiratory rate, and oral temperature after subject has been seated for 5 minutes.
- Record weight.
- Review and record AEs since last visit.
- Review and record any current concomitant medication use (including OTC, vitamins, and supplements).
- Perform a physical examination (excluding breast and genitourinary examination) with review of body systems.
- Collect blood and urine samples for central clinical laboratory tests (hematology, serum chemistry, urinalysis, thyroid panel, and serum ethanol); see Section 9.3.3.2.1 for a complete list of required laboratory tests.
- Collect urine for an on-site urine pregnancy test (if female).

•

- Collect all unused study drug dispensed at previous visit.
- Assess study drug compliance via drug accountability. Noncompliant subjects may be discontinued.
- •
- Administer evaluations:
 - \circ MADRS
 - o QIDS-SR-16
 - o CGI-S
 - o CGI-I
 - C-SSRS (since last visit)

9.1.6 Visit 9 (Day 49) / 1-Week Follow-up Phone Call

Visit 9 will be conducted by telephone. Any clinical findings observed during Visit 8 including clinically significant laboratory abnormalities, will be followed until the condition returns to prestudy status, has resolved or stabilized, or can be explained as being unrelated to the study drug. An in-clinic follow-up visit, if one should be necessary, will take place within 30 days of study drug termination.

If a subject is not able to continue treatment with study drug for any reason, he or she will be discontinued from treatment and if possible the procedures as listed in Visit 9 will be completed 1 week after the last dose of study drug.

At Visit 9, the following procedures will be performed:

- Review and record AEs since last visit.
- Review and record any current concomitant medication use (including OTC, vitamins, and supplements).
- Administer C-SSRS (since last visit).

9.2 Study Duration

The study will last up to approximately 11 weeks (including a Screening period up to 4 weeks, 6 weeks of treatment, and a 1-week follow-up period).

9.3 Assessments

The assessments listed below will be administered at the time points specified in the Schedule of Assessments in Section 17.2.

9.3.1.1 Structured Clinical Interview for DSM-5, Clinical Trials Version (SCID-5-CT)

The SCID-5-CT [9] is a clinician-rated diagnostic assessment that will be administered at Visit 1 and will be considered a source document in this study. The SCID-5 is an interview guide for making DSM-5 diagnoses and has been adapted for use in this protocol. The interview will be administered by the Investigator or a Sub-Investigator who is a psychiatrist, a doctoral or masters level clinical psychologist or a psychiatric nurse with sufficient experience in the diagnosis of mental illness.

9.3.1.2 Montgomery-Åsberg Depression Rating Scale (MADRS)

The MADRS [10] is a clinician-rated scale. The MADRS is used to assess depressive symptomatology during the previous week. Subjects are rated on 10 items to assess feelings of sadness, lassitude, pessimism, inner tension, suicidality, reduced sleep or appetite, difficulty concentrating and lack of interest. Each item is scored on a 7-point scale. A score of 0 indicates the absence of symptoms, and a score of 6 indicates symptoms of maximum severity.

9.3.1.3 Quick Inventory of Depressive Symptomology – Self-Rated (QIDS-SR-16)

The 16-item QIDS-SR-16 [11], a patient-rated scale, is an abbreviated version of the 30-item Inventory of Depressive Symptomatology (IDS) and is designed to assess the severity of depressive symptoms. The QIDS-SR-16 assesses criterion symptom domains to diagnose a major depressive episode.

The QIDS-SR will be used to assess the subject's depressive symptomatology over the past 7 days. Subjects report severity of symptoms on 10 items assessing sleep, feelings of sadness, appetite, weight change, concentration, self-regard, suicidality, general interest level, energy level, psychomotor retardation, and restlessness. Each item will be scored on a 4-point scale with a score of 0 reflecting no symptoms and a score of 3 reflecting symptoms of maximum severity.

9.3.1.4 Clinical Global Impression – Severity (CGI-S)

The CGI-S scale [12] is a clinician-rated scale used to rate the severity of the subject's current state of mental illness compared with a subject population with MDD. The subject is rated on a scale from 1 to 7, with 1 indicating a "normal state" and 7 indicating "among the most extremely ill subjects." The CGI-S will be administered by the Investigator or a Sub-Investigator with extensive professional training and experience in assessing mental illness.

9.3.1.5 Clinical Global Impression – Improvement (CGI-I)

The CGI-I scale [12] is a clinician-rated scale that is used to rate total improvement or worsening of mental illness regardless of whether the Investigator considers it to be a result of drug treatment or not. The subject is rated on a scale from 1 to 7, with 1 indicating that the subject is very much improved and 7 indicating that the subject is very much worse. The CGI-I will be administered by the Investigator or a Sub-Investigator with extensive professional training and experience in assessing mental illness.

9.3.2 Clinical Pharmacology

9.3.3 Safety

Safety assessments will include the evaluation of TEAEs; clinical laboratory test results; vital sign measurements; and physical examination findings.

9.3.3.1 Adverse Events

The definitions and management of and special considerations for AEs are provided in Section 10.

9.3.3.2 Clinical Laboratory Safety Assessments

9.3.3.2.1 Clinical Laboratory Tests to Be Performed

Samples for the following laboratory tests will be collected at the time points specified in the Schedule of Assessments (Section 17.2).

Hematology	Hemoglobin, hematocrit, red blood cell count, red blood cell indices (mean corpuscular volume, mean corpuscular hemoglobin, mean corpuscular hemoglobin concentration), platelet count (or estimate), and white blood cell count (including differential), absolute and % Neutrophil, Lymphocyte, Basophil, Monocyte, and Eosinophils
Serum Chemistry	Albumin, total bilirubin, direct bilirubin, total protein, calcium, alkaline phosphatase, alanine aminotransferase, aspartate aminotransferase, blood urea nitrogen, creatinine, random glucose, sodium, potassium, chloride, C-reactive protein (CRP), cholesterol
Urinalysis	pH, specific gravity, blood, glucose, protein, ketones, and leukocyte esterase
Thyroid Panel	TSH, Free T3, Free T4
Urine Drug Screen	Benzoylecgonine (cocaine), barbiturates, amphetamines, benzodiazepines, cannabinoids, opiates, methadone, phencyclidine, ecstasy (MDMA)
Serum Ethanol Level	
Repeat Urine Drug Screen	May be performed at random during the study upon request of the investigator
Repeat Serum Ethanol Level	May be performed at random during the study upon request of the investigator

Other laboratory assessments may be repeated at any visit if there was an abnormal finding at the most recent previous evaluation or if additional information is clinically necessary to appropriately follow up and/or manage an adverse experience.

All blood and urine samples will be sent to a central laboratory for analyses.

9.3.3.2.2 Pregnancy Testing

Female subjects will be required to have an onsite urine pregnancy test at Visit 1, Visit 2 and Visit 8/ET.

A positive pregnancy test will exclude a subject from participating further in the study. In the event that a false positive is suspected, a repeat pregnancy test may be performed. Investigators should inquire at every study visit about the continued use of acceptable methods of contraception in

females of child-bearing potential and perform a repeat pregnancy test if there is any question of non-compliance with contraception.

9.3.3.2.3 Specimen Handling Requirements

The transmission of infectious agents may occur through contact with contaminated needles and blood or blood products. Consequently, appropriate blood and body fluid precautions should be employed by all study personnel involved in the collection of blood and handling of specimens in both the clinic and laboratory settings. Refer to current recommendations of the appropriate authorities.

In addition to appropriate handling of subject samples, specific regulations exist about the shipment of biologic/etiologic samples. Procedures and regulations for the packaging and shipping of infectious samples are outlined in the study laboratory manual. The Investigator is responsible for ensuring that all study samples that are to be transported to another location are appropriately packed and shipped according to the applicable regulations.

9.3.3.2.4 Evaluation of Clinical Laboratory Values

The normal ranges of values for clinical laboratory assessments in this study will be provided by the responsible laboratory and submitted to Axsome or its designee before the start of the study. These will be regarded as the reference ranges on which decisions will be made.

If a clinical laboratory value is out of the reference range, it is not necessarily clinically relevant. The Investigator is responsible for determining whether these occurrences are considered as AEs.

All clinical laboratory values that in the Investigator's opinion show clinically relevant or pathological changes during or after termination of the treatment must be reported as AEs and followed as described in Section 10.2.5.

All measurements described in this section are recognized standard methods.

9.3.3.3 Clinical Examinations

9.3.3.3.1 Vital Signs

Vital signs will include seated blood pressure, pulse, respiratory rate, and oral temperature. Seated blood pressure and other vital signs will be measured after the subject has been in a sitting position for 5 minutes.

9.3.3.3.2 Physical Examination

A complete physical examination (excluding breast and genitourinary examination) will be performed at Screening by a licensed physician or clinician (NP, DO, PA) and at the final on-site visit (Visit 8/ET). Physical examination will include assessments of head, eyes, ears, nose, throat, lymph nodes, skin, extremities, respiratory, gastrointestinal, musculoskeletal, cardiovascular, and nervous systems. The physical examination should be performed by the same person each time, whenever possible. Physical examination abnormalities determined by the Investigator to be clinically significant at Screening should be recorded as medical history. The thoroughness of the Visit 8/ET physical examination is at the discretion and judgment of the Investigator, but should include a brief review of systems to ensure there have been no changes since Screening.

9.3.3.3.3 Other Safety Assessments

9.3.3.3.3.1 Columbia Suicide Severity Rating Scale (C-SSRS)

The C-SSRS [14] is a clinician-rated instrument that reports the severity of both suicidal ideation and behavior. Suicidal ideation is classified on a 5-item scale: 1 (wish to be dead), 2 (nonspecific active suicidal thoughts), 3 (active suicidal ideation with any methods [not plan] without intent to act), 4 (active suicidal ideation with some intent to act, without specific plan), and 5 (active suicidal ideation with specific plan and intent). The C-SSRS also captures information about the intensity of ideation, specifically the frequency, duration, controllability, deterrents, and reasons for the most severe types of ideation. Suicidal behavior is classified on a 5-item scale: 0 (no suicidal behavior), 1 (preparatory acts or behavior), 2 (aborted attempt), 3 (interrupted attempt), and 4 (actual attempt). More than 1 classification can be selected provided they represent separate episodes. For actual attempts only, the actual or potential lethality is classified for the initial, most lethal, and most recent attempts.

The C-SSRS will be completed at Visits 1, 2, and 4 - 9. At Visit 1 (Screening) the C-SSRS will be completed for the subject's lifetime history of suicidal ideation and behavior, along with a recent recall period. At all other visits the C-SSRS will be completed for ideation and behavior with a recall period since the last visit.

The C-SSRS will be administered by the Investigator.

10. ADVERSE EVENTS

10.1 Definitions

10.1.1 Adverse Events

An AE is defined as any untoward medical occurrence in a subject or clinical investigation subject administered a pharmaceutical product that does not necessarily have a causal relationship with the product. An AE can therefore be any unfavorable and unintended sign (including a new, clinically important abnormal laboratory finding), symptom, or disease, temporally associated with the product, whether or not related to the product.

Pre-existing diseases or conditions will not be considered AEs unless there is an increase in the frequency or severity, or a change in the quality, of the disease or condition. (Worsening of a pre-existing condition is considered an AE.)

Events that occur in subjects treated with active comparator or during treatment-free periods of the study are also considered AEs.

Clinical AEs should be described by diagnosis and not by symptoms when possible (e.g., cold, seasonal allergies, instead of "runny nose").

Please note medical procedures scheduled prior to consenting, but occurring during the study should not be captured as AEs, but should be listed in the medical history if related to a pre-existing condition.

10.1.2 Adverse Drug Reaction

All noxious and unintended responses to a study drug related to any dose should be considered adverse drug reactions (ADRs).

The phrase "responses to a study drug" means that a causal relationship between a study drug and an AE is at least a reasonable possibility, i.e., the relationship cannot be ruled out. All AEs judged by either the reporting Investigator or the Sponsor as having a reasonable causal relationship to a study drug qualify as ADRs.

All AEs for which the judgment of relationship to the study drug is "possible" or higher will be considered ADRs. If a relationship to the study drug is not given, then the AE must be treated as if the relationship to the study drug were "possible."

10.1.3 Unexpected Adverse Event/Adverse Drug Reaction

An expected AE or ADR is an event for which the nature or severity is consistent with the known AE profile of the product. For a study drug, the known information is contained in the IB and in the current package inserts for marketed drugs that contain the same active moiety. For a marketed product, the known information is contained in the current package insert for the product.

An unexpected adverse event (UAE) or unexpected adverse drug reaction (UADR) is an event for which the specificity or severity is not consistent with the current IB. For example, hepatic necrosis would be unexpected (greater severity) if the IB only listed elevated hepatic enzymes or hepatitis. Likewise, cerebral thromboembolism and cerebral vasculitis would be unexpected (greater specificity) if the IB only listed cerebral vascular accidents.

Furthermore, reports that add significant information on specificity or severity of a known, already documented adverse reaction constitute unexpected events. Examples would be a) acute renal failure as an expected adverse reaction with a subsequent new occurrence of interstitial nephritis (interstitial nephritis would be unexpected) and b) hepatitis with a first occurrence of fulminant hepatitis (fulminant hepatitis would be unexpected.)

10.1.4 Serious Adverse Events/Drug Reaction

A serious adverse event (SAE) is any untoward medical occurrence that at any dose:

- Results in death.
- Is life-threatening.

NOTE: The term "life-threatening" in the definition of "serious" refers to an event in which the subject was at risk of death at the time of the event; it does not refer to an event which hypothetically might have caused death if it were more severe.

- Requires inpatient hospitalization or prolongation of existing hospitalization. NOTE: Inpatient hospitalization is defined as 24 hours in a hospital or an overnight stay. An elective hospital admission to treat a condition present before exposure to the study drug, or a hospital admission for a diagnostic evaluation of an AE, does not qualify the condition or event as an SAE. Further, an overnight stay in the hospital that is only due to transportation, organization, or accommodation problems and without medical background does not need to be considered an SAE.
- Results in persistent or significant disability/incapacity.
- Is a congenital anomaly.

NOTE: A congenital anomaly in an infant born to a mother who was exposed to the study drug during pregnancy is an SAE. However, a newly diagnosed pregnancy in a subject who has received a study drug is not considered an SAE unless it is suspected that the study drug(s) interacted with a contraceptive method and led to the pregnancy.

• Is an important medical event.

NOTE: Medical and scientific judgment should be exercised in deciding whether it is appropriate to consider other situations serious, such as important medical events that may not be immediately life-threatening or result in death or hospitalization but may jeopardize the subject or may require intervention to prevent 1 of the other outcomes listed in the definition above. Examples of such events are intensive treatment in an emergency room or at home for allergic bronchospasm, blood dyscrasias or convulsions that do not result in hospitalization, or development of drug dependency or drug abuse. The occurrence of malignant tumors is also to be considered serious.

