7.2 Study Entry Criteria

7.2.1 Inclusion Criteria

A subject will be eligible for study participation if the subject meets all of the following criteria:

- 1. Provides written informed consent to participate in the study, is able to understand the procedures and study requirements, and agrees to abide by the study restrictions and return for the required study assessments.
- 2. Male or female outpatients, 18 to 65 years of age, inclusive.
- 3. Currently meets the DSM-5 criteria for MDD without psychotic features, based on the SCID-

5-CT, with a current major depressive episode of at leave 4 weeks in duration at Visit 1.

- 4. MADRS score of ≥ 25 and CGI-S ≥ 4 at Screening (Visit 1) and Baseline (Visit 2).
- 5. Normal physical examination findings and clinical laboratory test results from Screening (Visit 1) or abnormal results that are judged not clinically significant by the investigator.
- 6. Body mass index (BMI) between 18 and 40 kg/m², inclusive.
- 7. If female of childbearing potential, having a negative urine pregnancy test result at Visit 1 and Visit 2, and practicing an adequate method of birth control (e.g. oral or parenteral contraceptives, intrauterine device, double-barrier) and does not plan to become pregnant during the course of the study. Long-term abstinence is acceptable as long as the subject agrees to use double-barrier contraception if they decide to have sexual intercourse. Female subjects using a hormonal contraceptive or intrauterine device must have been doing so for at least 1 month before Screening and must follow that product's package insert instructions including additional protection at times when hormonal contraceptive doses might be missed. Female subjects may be included without a negative urine pregnancy test if they are surgically sterile or at least 2 years post-menopausal. Male subjects and their female sexual partners should use an acceptable method of birth control (as noted above) during the study.

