10.2.6 Notification

10.2.6.1 Serious Adverse Events

The Investigator or designee must report all SAEs promptly to within 24 hours of first becoming aware of the event by completing the SAE Report Form and faxing or emailing it to number or email shown below. Axsome's Medical Monitor may also be notified by telephone. Even if an initial report is made by telephone, the SAE Report Form must be completed with all available details and faxed within 24 hours of knowledge of the event at the study site.

At the time of first notification, the Investigator or designee should provide the following information, if available:

- Protocol number.
- Reporter (study site and Investigator).
- Subject's study number and initials.
- Subject's date of birth.
- Subject's gender.
- Date of first dose of study drug(s).

Axsome Therapeutics, Inc. AXS-05-MDD-201

- Date of last dose of the study drug(s), if applicable.
- Adverse event term.
- Time and date of occurrence of the event.
- A brief description of the event, outcome to date, and any actions taken.
- The seriousness criteria (on) that were met.
- Concomitant medication at onset of the event.
- Relevant past history information.
- Relevant laboratory test findings.
- Investigator's opinion of the relationship to the study drug(s).
- Whether and when the Investigator was unblinded as to the subject's treatment assignment.

The Investigator must fax or e-mail a written SAE Report Form that describes the SAE to the recipient(s) of the initial information, who will forward the information to Axsome. The Investigator must also immediately deliver any available supporting information requested on the SAE Report Form or by Axsome.

Any missing or additional relevant information concerning the SAE should be provided to the recipient(s) of the initial information in a written, follow-up SAE Report Form. Supplemental information should be submitted as soon as available and may include laboratory results, radiology reports, progress notes, hospital admission and emergency room notes, holding and observation notes, discharge summaries, autopsy reports, and death certificates.

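### The elective-admission note in Protocol 10.1.4 has no limit for worsened conditions, so an elective admission for depression that worsened after dosing need not be an SAE on the ground of hospitalization

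*Protocol*

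**What the plan says.** Protocol 10.1.4 lists as one route to seriousness an event that "Requires inpatient hospitalization or prolongation of existing hospitalization". The note under that bullet removes some admissions from the route. One of them is "An elective hospital admission to treat a condition present before exposure to the study drug"; for these, the note says that neither the condition nor the event becomes an SAE.

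Protocol 10.1.1 deals with pre-existing conditions in two separate statements. The first is a rule on change: "Worsening of a pre-existing condition is considered an AE". The second is an exemption for planned care: "medical procedures scheduled prior to consenting, but occurring during the study should not be captured as AEs". Neither limit appears in the 10.1.4 note.

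Inclusion criterion 3 (Protocol 7.2.1) requires that each subject "Currently meets the DSM-5 criteria for MDD without psychotic features". The study disease is therefore present before exposure in everyone.

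Serious events must be reported "within 24 hours of first becoming aware of the event" (Protocol 10.2.6.1). Non-serious events are reviewed by the sponsor on a regular basis (10.2.6.3).

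**The concern.** The note applies two tests: whether the admission is elective, and whether the condition predates dosing. In most trials the second test mainly catches comorbidities. Here it also catches the disease under treatment. A psychiatric admission arranged during the treatment period because depression has deteriorated can pass both tests.

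Such an admission matters in this trial for three reasons. Safety and tolerability is the only objective that the protocol states (Section 5). Exclusion criterion 6 bars subjects who have had a psychiatric hospitalization in the current episode, so an admission for that episode after randomization is a change from entry status. And there is no data safety monitoring board (Section 11) and no list of adverse events of special interest (10.3.1), which leaves SAE classification as the main route to prompt sponsor review.

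If the event is classed as non-serious, the 24-hour report is lost, and the event is left out of the SAE listing (Protocol 12.4.3.1) and the SAE tables (SAP 10.2). If it is judged drug-related, reporting to health authorities moves from immediate to after study completion (Protocol 10.2.6.2).

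**Working it through.** No arithmetic applies, because the point concerns the wording of a definition. The check is to apply 10.1.1 and the 10.1.4 note to the same four situations and see where they diverge.

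| Situation after dosing | Adverse event under 10.1.1? | Exempt under this limb of the 10.1.4 note? | Meets the hospitalization criterion? |
|---|---|---|---|
| Urgent admission, depression worsened | Yes | No, not elective | Yes |
| Elective admission, condition that began after dosing | Yes | No, not present before exposure | Yes |
| Elective admission, pre-existing condition unchanged | No | Yes | No |
| Elective admission, depression worsened | Yes | Yes, on the literal wording | No |

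(The note's other exemptions, for diagnostic evaluation and for logistical overnight stays, are set aside.)

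1. In the first three rows the sections agree: where 10.1.1 sees an adverse event, the admission counts, and where it sees none, the admission does not.
2. The fourth row breaks the pattern. 10.1.1 treats the worsening as an adverse event in its own right, and 10.1.5 counts worsening after the first dose as treatment emergent. The note nevertheless takes the resulting admission out of the hospitalization criterion, because it looks only at when the condition began.
3. Inclusion criterion 3 means that any randomized subject could fall in the fourth row for the study disease. How many will do so depends on how many have an elective admission, which the documents do not say.
4. The protocol does not define *elective*. Whether a voluntary or arranged psychiatric admission is elective is left to each of up to 5 sites (Protocol 6.3), so identical events could be placed in row one at one site and row four at another.

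**The case against.** The strongest reply is that the note closes only one of several routes. Death, threat to life, disability and the important-medical-event criterion remain, and for the last of these "Medical and scientific judgment should be exercised in deciding whether it is appropriate to consider other situations serious". This stands. It rules out the stronger inference that an arranged admission for worsened depression can never be an SAE. The important-medical-event route is a weak backstop, however: it is discretionary, and its note is written for events that did not lead to hospitalization.

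A second reply is that an admission required by deterioration is not really elective, and that worsening, being a new event under 10.1.1, was not present before exposure. Both readings are reasonable, so the text is ambiguous and does not establish an exclusion. But the note exempts the event as well as the condition, which favours the literal reading, and expedited reporting should not depend on how a site resolves the question.

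A third reply is that the event stays visible. The worsening is recorded as an adverse event, suicidality is rated on the C-SSRS at nearly every visit, and SAP 10.2 summarizes hospitalizations by group. This also stands, but none of it restores SAE status or the 24-hour report. The documents do not say where the hospitalization count comes from. The adverse event items in Protocol 10.2.3 mention hospitalization only as an example of seriousness, so an exempt admission might be missed there too; that is an inference.

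**Conclusion.** The gap is real but narrow. On the literal wording, an elective admission for depression, or for any comorbidity, that worsened after dosing need not be reported as an SAE because of the hospitalization. The consequence is possible loss of 24-hour reporting and of entry in the SAE tables, with classification that may differ between sites. This assumes that the site regards the admission as elective and that no other seriousness criterion is applied.

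The size cannot be given as a rate, because the documents state no expected number of admissions. Two further inferences are tempting and are not supported:

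- A reader might add that the event would fall outside the shorter window for non-serious events. Worsening with onset during treatment lies inside that window in both documents: through 7 days after the last dose in Protocol 12.4.3.1, and onset before the last dose in SAP 10.2. The windows matter only for later onsets.
- A reader might take one missed SAE as 1/30 = 3.3 percentage points of an arm. The 30 per arm in Protocol 12.2 are compliant completers, whereas safety rates use the Safety Population of all dosed subjects (12.3), so 30 is the wrong denominator.

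The point is a cheap improvement to safety reporting and does not show that the trial's safety data would be unsound.

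**What to change.** Reconcile 10.1.4 with 10.1.1. Limit the exemption to elective admissions for a pre-existing condition that has not worsened since consent. State that an admission for worsening of a pre-existing condition, including major depressive disorder, meets the hospitalization criterion. Consent is a suitable reference point because adverse event collection starts there (Protocol 10.2).

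Do not also require that the admission was scheduled before consent. In 10.1.1 that condition governs medical procedures, and the worsening rule carries no scheduling test. Adding it would turn an elective admission arranged after consent for an unchanged condition into an SAE, although 10.1.1 does not count an unchanged condition as an adverse event at all.

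The cost is one sentence in 10.1.4, matching text in the SAE form instructions, and possibly a few more SAE reports. It changes how events are reported and leaves clinical care as it is.
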